5.5.3 Labelling

Labels will be prepared in accordance with Good Manufacturing Practice (GMP) and local regulatory guidelines. The labels will fulfil GMP Annex 13 requirements for labelling. Label text will be translated into local language.

5.5.4 Storage

The IP will be shipped to study sites and stored under controlled temperature: 2-8°C.

All study drugs should be kept in a secure place under appropriate storage conditions. The IP label on the study kit specifies the appropriate storage. IP must be kept in the original outer package in a secure area with restricted access.

The IP must not be frozen. It is preferred that an on-site refrigerator has an electronic temperature monitoring system or chart recorder. At minimum, the on-site refrigerator must have daily monitoring of the minimum/maximum temperature.

5.6 Concomitant and post-study treatment(s)

Medications considered necessary for the patient's safety and well being with the exception of drugs listed in section 5.1, may be given at the discretion of the investigator. Concomitant medications must be recorded in the appropriate sections of the eCRF.

Patients must be instructed not to take any medications, including over-the-counter products, without first consulting with the investigator.

5.6.1 Background medications

IP will be given as add-on medication for patients treated for UC according to the local standard of care. Accepted background medications for UC are:

- 5-ASA containing medications,
- purine analogues (azathioprine or mercaptopurine), and/or
- low dose glucocorticosteroids (\leq 20 mg oral prednisolone or equivalent daily).

All enrolled patients must receive at least 5-ASA containing medications, with the exception of patients refractory to 5-ASA containing medications or unable to tolerate 5-ASA containing medications (see section 4.1 Inclusion criteria, bullet 5).

Administration of IP must be discontinued if intensified therapy for UC is regarded medically necessary by the investigator (see section 5.8, bullets 7a and 7b). Intensified therapy includes surgery for UC, increased daily doses of background therapy for UC or the addition of any

new therapies for UC (listed in section 5.6.2). Intensified therapy should be according to the local standard of care considering the patients condition.

The daily doses of background therapy for UC may be decreased in response to clinical improvement or tolerability issues, as per local standard of care. The daily dose of background therapy for UC may not be increased, see previous paragraph.

The background UC medication is not regarded as study drug, and will not be provided by AstraZeneca or MedImmune.

5.6.2 Prohibited medications during study

Medication not allowed from Visit 1 and throughout the study:

- Drugs which affect GI pathology, function and integrity, including NSAIDs (with the exception of occasional use up to 1 day/week),
- Antibiotics (except for treatment of acute illness),
- Intravenous glucocorticosteroids,
- Oral glucocorticosteroids at a daily dose higher than the daily dose administered during the enrolment period,
- Anti-TNFs,
- Immunosuppressives (excluding the background medications specified in section 5.6.1),
- Interferons,
- Immunoglobulin or blood products,
- Live attenuated vaccines.

Administration of IP must be discontinued if prohibited medications are to be administered to the patient (see section 5.8, particularly bullets 7a and 7b).

5.7 Treatment compliance

The administration of all IP should be recorded in the appropriate sections of the eCRF.

IP is administered during study visits by study site staff, who will monitor compliance.

5.7.1 Accountability

MedImmune will provide the investigators with IP using designated distribution centers. MedImmune will provide the investigator(s) with adequate stock quantities of IP and the stock

levels will be maintained via the IVRS/IWRS as vials are used. The study drug provided for this study will be used only as directed in the study protocol.

The unblinded IP Manager/pharmacist is required to maintain accurate IP accountability records. The study staff will account for all study drugs dispensed to patients. Upon completion of the study, copies of IP accountability records will be returned to AstraZeneca. As per the MedImmune 's procedures unused IP will be returned to the local depot and destroyed upon authorization by the MedImmune.

Study site staff, if applicable, or the AZ monitor will account for all study drugs received at the site, unused study drugs and for appropriate destruction. Certificates of delivery and destruction should be signed.

5.8 Discontinuation of Investigational Product

Patients may be discontinued from IP in the following situations:

1. Patient decision. The patient is at any time free to discontinue treatment, without prejudice to further treatment,
2. Incorrect enrolment (i.e., the patient does not meet the required inclusion/exclusion criteria),
3. Pregnancy,
4. Experienced an event, which in the opinion of the investigator and/or AstraZeneca, contraindicated further dosing such as illnesses or complications, e.g. anaphylactic reaction to the IP or other safety reasons,
5. Adverse Event,
6. Severe non-compliance to study protocol,
7. Development of any study specific criteria for discontinuation:
 - (a) Patient with insufficient therapeutic response and thus in need of intensified therapy for UC prescribed at the discretion of the investigator,
 - (b) Patient with insufficient therapeutic response or in need of surgery.

5.8.1 Procedures for discontinuation of a patient from investigational product

A patient who decides to discontinue IP will always be asked about the reason(s) and the presence of any adverse events.

If the patient is discontinued from IP, the scheduled study visits, data collection and procedures should continue according to the study protocol until study completion. Alternatively, if the patient does not agree to this option, a modified follow up through eg,

regular telephone contacts or a contact at study completion should be arranged, if agreed to by the patient and in compliance with local data privacy laws/practices. The approach taken should be registered in the eCRF.

If a patient is withdrawn from study, see Section 5.9.

5.9 Withdrawal from study

Patients are at any time free to withdraw from study (IP and assessments), without prejudice to further treatment (withdrawal of consent). Such patients will always be asked about the reason(s) and the presence of any adverse events. If possible, they will be seen and assessed by an investigator. Adverse events will be followed up (See Sections 6.4.3 and 6.4.4) and the patient should return diary cards.

Withdrawn patients will not be replaced.

6. COLLECTION OF STUDY VARIABLES

6.1 Recording of data

The Rave Web Based Data Capture (WBDC) system will be used for data collection and query handling. The investigator will ensure that data are recorded on the electronic Case Report Forms as specified in the study protocol and in accordance with the instructions provided.

The principal investigator ensures the accuracy, completeness and timeliness of the data recorded and of the provision of answers to data queries according to the Clinical Study Agreement. The principal investigator will sign the electronic Case Report Form. A copy of the completed electronic Case Report Forms will be archived at the study site.

Data from the central laboratories assessments will be either loaded into WBDC or returned to AstraZeneca directly as datasets, and validated to ensure that it is consistent with the clinical data. Any queries on the data will be raised and resolved within the WBDC system or other designated systems.

6.1.1 Diary Card

Patients will collect information in a Diary Card related to symptoms of ulcerative colitis and changes in concomitant medications from the Enrolment Visit and continuing throughout the study. The Diary Card is aimed to facilitate for the patient to remember his/her symptoms of disease and any change in concomitant medication. The Diary Cards will be reviewed at every visit by the investigator. Information entered by the patient in the Diary Card will facilitate recording data needed to determine the partial Mayo score.

6.2 Data collection at enrolment and follow-up

6.2.1 Enrolment procedures

During the enrolment period (up to randomisation) the following data will be collected and recorded in the appropriate sections of the eCRF:

- Demographics (including sex, date of birth /or age), race and/or ethnic group
- Medical and surgical history
- Nicotine use (current/former/never user)
- Concomitant medications
- Physical examination, vital signs, weight, and height measurements
- 12-lead ECG
- Disease specific characteristic
- Mayo score and Partial Mayo score (see Section [6.3.1](#)) from baseline endoscopy examination
- Modified Riley score reading local and central ([Geboes et al 2000](#)) from biopsies collected during baseline endoscopy
- Collection of blood, urine, and faeces samples for laboratory variables listed in [Table 8](#), [Table 9](#), and [Table 10](#).
- Urine pregnancy test for females of childbearing potential
- Completion of UCGHQ
- Adverse Events and Serious Adverse Events.

6.2.2 Follow-up procedures

During the follow-up period from Visit 9 to Visit 11, the following data will be collected according to Study Plan ([Table 1](#)):

- Physical examination, vital signs, and weight measurements
- Partial Mayo score
- Completion of UCGHQ
- 12-lead ECG

- Collection of blood, urine, and faeces samples for laboratory variables listed in [Table 8](#), [Table 9](#), and [Table 10](#).
- Urine pregnancy test for females of childbearing potential
- Concomitant medications
- Adverse Events and Serious Adverse Events.

6.3 Efficacy

6.3.1 Mayo Score

The investigator will assess Mayo score at Visit 2 (baseline) and at Visit 6 (Week 8). Mayo score is a combined endpoint consisting of the summarized scoring from four sub-score areas: stool frequency, rectal bleeding, endoscopy findings and the physician's overall assessment of the same in addition to abdominal discomfort and patient's general sense of well-being. The below scoring system will be used ([Lewis et al 2008](#), and [Schroeder et al 1987](#)):

Stool frequency (Each patient serves as his or her own control to establish the degree of abnormality of the stool frequency)

- | | |
|---|--|
| 0 | Normal number of stools per day for this patient |
| 1 | 1-2 stools per day more than normal |
| 2 | 3-4 stools per day more than normal |
| 3 | 5 or more stools per day more than normal |

Rectal bleeding (The daily bleeding score represents the most severe bleeding of the day)

- | | |
|---|---|
| 0 | No blood seen |
| 1 | Streaks of blood with stool less than half the time |
| 2 | Obvious blood with stool most of the time |
| 3 | Blood alone passes |

Findings of endoscopy

- | | |
|---|---|
| 0 | Normal or inactive disease |
| 1 | Mild disease (erythema, decreased vascular pattern, mild friability) |
| 2 | Moderate disease (marked erythema, absent vascular pattern, friability, erosions) |
| 3 | Severe disease (spontaneous bleeding, ulceration) |

Physician's global assessment (PGA) (The physician's global assessment acknowledges the 3 other criteria, the patient's recall of abdominal discomfort and general sense of well-being)

- | | |
|---|------------------|
| 0 | Normal |
| 1 | Mild disease |
| 2 | Moderate disease |
| 3 | Severe disease |

Mayo score is assessed on the study visit day by the following procedure:

- For stool frequency and rectal bleeding the average symptom severity over the previous 3 days as reported in the Diary Card and during the visit is used to calculate the Mayo score. Diary Cards will be used for daily recording of symptoms between visits.
- Endoscopy subscore represents the endoscopy conducted on the study visit day.

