3.2.4 Dosing and study duration

In study MI-CP199 tralokinumab 150mg, 300mg and 600mg sc was administered to patients with moderate to severe asthma. FEV₁ showed a trend to improve in all treatment arms

compared with placebo, but FEV₁ was similar in the 300mg and 600mg treatment arms. FEV₁ improved more in the 300mg and 600mg treatment arms than in the 150mg treatment arm. Tralokinumab was associated with acceptable safety profile at all three doses, but the incidence of diarrhoea was significantly higher in the 600mg arm than in the 150mg and 300mg arms. See the tralokinumab IB for further details on efficacy and safety in study MI-CP199.

The PK/PD profile for tralokinumab has not been defined in UC, but is assumed to be similar to that in asthma. Since the 600mg dose was associated with an increased incidence of diarrhoea, which is a particularly undesirable adverse effect in UC, and since efficacy measured as FEV₁ was similar at 300mg and 600mg in study MI-CP199, the 300mg dose was selected for this study.

The primary endpoint will be assessed at 8 weeks to provide efficacy results comparable to other biologic drugs approved or in development for the treatment of UC.

Treatment will continue for 12 weeks to ensure the tralokinumab steady state is achieved, which will provide a better understanding of the safety profile of tralokinumab to be expected during long-term administration to patients with UC.

The 12-week safety follow-up after the last IP administration is appropriate given the pharmacokinetic profile of tralokinumab demonstrated in previous studies. Also efficacy parameters will be collected for 12 weeks beyond the last IP administration, since a previous asthma study (MI-CP199) suggested tralokinumab efficacy may be prolonged beyond what would be expected based on PK data (IB section 5.1.2.1.1.2).

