6.3.2 Endoscopy

Endoscopic assessments are scheduled during the enrolment period (baseline) and Visit 6 at week 8. Colonoscopy is the preferred procedure, but if the full extent of the disease can be assessed and unaffected mucosa can be visualized, and photographs and biopsies can be taken using flexible sigmoidoscopy, then flexible sigmoidoscopy is an acceptable alternative. Flexible sigmoidoscopy is not an acceptable alternative under any other circumstances.

Patients will be prepared for endoscopy according to local practice. All medications administered in preparation for and during the endoscopy will be recorded as concomitant medications in the eCRF.

Photographs will be taken of the areas from which biopsies are collected. The photographs will not have to be submitted to the sponsor, unless specifically requested, but should remain archived at the study site. The photographs may be reviewed at site by study monitors or auditors. The study sponsor will request copies of the photographs to be submitted for central

review and adjudication if the central pathology assessment of the collected biopsies does not align with the reported Mayo endoscopy scores reported in the eCRF.

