6.3.2.1 Biopsy sampling

Biopsies will be collected during both endoscopies, but only if biopsy collection is not associated with significant discomfort or unacceptable medical risk to the individual patient.

The handling and shipping of the collected biopsy specimen is detailed in the Laboratory Manual.

Biopsies will be collected from areas with active disease/macrosopic inflammation, as well as from unaffected mucosa.

Biopsies for local assessment of disease histology

A biopsy will be collected from affected mucosa to allow local assessment of disease histology. Additional biopsies may be collected, e.g. for mapping of the extent of disease or assessment of incidentally found polyps, if required by local standard of care. The histology will be assessed according to a modified Riley score ([Riley et al 1991](#), and [Geboes et al 2000](#)) to evaluate the disease activity, and will be recorded in the eCRF. If multiple biopsies are collected the highest score achieved by any biopsy should be reported on the eCRF. The baseline biopsy will also be used to confirm the UC diagnosis. The patient is not eligible to be randomised if the histology findings do not support a diagnosis of UC. Assessment of presence or absence of cytomegalovirus (CMV) infection by the local pathology laboratory is encouraged whenever such an infection is suspected.

The pathology report must be reviewed and signed by the investigator.

Biopsy sampling for central analysis

Six biopsies will be collected for central analysis from each patient at each endoscopy:

- Three in an area exhibiting active disease/macrosopic inflammation at baseline,
- Three in an area unaffected by disease/without macrosopic inflammation at baseline.

Biopsies should be collected from the same area of the intestine at baseline and at Visit 6 (week 8), whether the macroscopic appearance of the mucosa has changed between baseline and Visit 6 (week 8) or not.

Biopsies from the unaffected mucosa will not need to be collected if the patient exhibits pancolitis, and no unaffected mucosa can be found.

The outcome of the central histology assessment will be entered into the eCRF, but will not influence patient study participation.

One or more of the collected biopsies will be utilized to examine if CMV infection is present in the mucosa, either by PCR or by immunohistochemistry, or both. The treating physician will be informed if CMV infection is suspected.

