11.1.4 Clinical remission at week 8 based on Mayo score

A patient will be classified as being in clinical remission if both the criteria below are fulfilled at week 8:

- Absolute Mayo score ≤ 2
- No individual subscore > 1

A patient discontinuing IP, requiring intensified therapy, or who underwent a colectomy or ostomy before week 8, or who has a missing Mayo score registration at week 8, will be classified as in no remission.

11.1.5 Mucosal healing at week 8

Mucosal healing is defined as an improvement of the endoscopy sub-score (from the Mayo score) at week 8 from 3 or 2 to ≤ 1 point, or from 1 to 0 points.

A patient discontinuing IP, requiring intensified therapy, or who underwent a colectomy or ostomy before week 8, or who has missing endoscopy sub-score registration at week 8, will be classified as not have had mucosal healing.

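### Where oral bowel preparation is taken the day before, the week-8 stool sub-score counts the preparation day and can be too high in patients who improved

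*Protocol*

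**What the plan says.** **Symptom window.** Section 6.3.1 has the investigator assess the Mayo score at Visit 2 and Visit 6. For two of the four sub-scores the rule reads: "For stool frequency and rectal bleeding the average symptom severity over the previous 3 days as reported in the Diary Card" and during the visit. No day is left out, no replacement day is named, and no rule says how a fractional average becomes a score of 0 to 3.

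**Endoscopy.** The same section adds: "Endoscopy subscore represents the endoscopy conducted on the study visit day". Section 6.3.2 says: "Endoscopic assessments are scheduled during the enrolment period (baseline) and Visit 6 at week 8". It prefers colonoscopy, allows flexible sigmoidoscopy only under conditions, and states: "Patients will be prepared for endoscopy according to local practice". Preparation drugs are recorded as concomitant medication. Nothing links them to the diary or the score.

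**Baseline.** The baseline endoscopy follows negative infection screening and precedes randomisation. Local histology also matters (6.3.2.1): "The patient is not eligible to be randomised if the histology findings do not support a diagnosis of UC".

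**Endpoints.** Response (11.1.3) needs a fall of at least 3 points and at least 30%, plus a rectal-bleeding criterion. Remission (11.1.4) needs a total of 2 or less and "No individual subscore > 1". By Table 1, the partial Mayo scores at Visits 2 and 6 are taken from the Mayo score.

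**The concern.** A day of laxative-induced stools says nothing about colitis, yet the rule gives it one third of the weight in the week-8 stool sub-score. It matters most when the other two days are good, so the misclassification falls mainly on patients who improved. It adds noise to the primary score and bears hardest on remission, which is tested with its own one-sided p-value (12.2, 12.2.2.1).

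The change from baseline may also not be like for like, because the preparation day can lie outside the Visit 2 window but, with day-before preparation, lies inside the Visit 6 window. In the repeated-measures analysis of partial Mayo (12.2.2.3), week 8 is the only post-baseline visit with an endoscopy. A bump there would be an artefact that weeks 4, 12, 16, 20 and 24 do not share.

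This is hard to repair at analysis. The investigator sets the sub-score at the visit, and section 6.1.1 describes the diary as an aid to that: "The Diary Card is aimed to facilitate for the patient to remember his/her symptoms of disease". The concomitant-medication record can show who was affected, but it does not give the sub-score they should have had.

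**Working it through.** **1. The plan's own figure.** Section 12.3 assumes 65% vs 35%, one-sided 0.05 and 90% power. Without continuity correction, n₀ = [1.645·√(2·0.5·0.5) + 1.282·√(0.65·0.35 + 0.35·0.65)]² / 0.30² = 45.7, so 46. With correction, (45.7/4)·[1 + √(1 + 4/(45.7·0.30))]² = 52.1, so 53 per arm, as stated. The 110 randomised patients give 55 per arm. Without continuity correction, power is Φ{[0.30·√55 − 1.645·√0.5] / √0.455} = Φ(1.57) = 94%. This is the reference below.

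**2. Effect on the stool sub-score.** Let s be the true daily score and score the preparation day 3 (assumption). The average is (s + s + 3)/3. Alternatively a site may average stool counts; take 8 extra stools on the preparation day (assumption), so that a true 0 becomes 8/3 = 2.67 extra stools, sub-score 2.

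| True score | Average of daily scores | Nearest integer | Truncated | Count averaging |
|---|---|---|---|---|
| 0 | 1.00 | 1 | 1 | 2 |
| 1 | 1.67 | 2 | 1 | 2 |
| 2 | 2.33 | 2 | 2 | 3 |
| 3 | 3.00 | 3 | 3 | 3 |

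When daily scores are averaged, only true scores of 0 or 1 can rise. When counts are averaged, a 2 can rise as well.

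**3. Remission patterns.** Four sub-scores of 0 or 1 summing to at most 2 give 1 + 4 + 6 = 11 patterns: 7 with stool 0 and 4 with stool 1.
- Nearest integer: only stool 0 with the other three summing to at most 1 survives, so 1 + 3 = 4 of 11.
- Truncation: stool 0 and stool 1 each keep 4, so 8 of 11.
- Count averaging: none for an affected patient.

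**4. Response example.** Baseline 3+2+2+2 = 9 and true week 8 1+1+2+2 = 6 (stool, bleeding, endoscopy, global assessment): fall 3, 33%, bleeding 1, a responder. With nearest-integer rounding, week 8 becomes 2+1+2+2 = 7: fall 2, a non-responder. With truncation the patient stays a responder.

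**5. Illustrative model (all inputs assumed).** Baseline stool 1/2/3 = 15/40/45%; bleeding 0/1/2/3 = 5/30/50/15%; endoscopy 2/3 = 55/45%; global assessment 2/3 = 75/25%; kept if Mayo is at least 6. Each week-8 sub-score is baseline minus a shared improvement (SD s) and separate noise (SD n), rounded and limited to 0–3. The mean improvement is set so that true response is 65% or 35%. All patients are affected at week 8, with a clean baseline, nearest-integer rounding and 55 per arm.

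| (s, n) | Response with preparation day | True remission | Remission with preparation day | Remission power |
|---|---|---|---|---|
| (0.6, 0.5) | 59.4 vs 29.9% | 15.6 vs 4.3% | 6.5 vs 1.4% | 64% to 39% |
| (0.8, 0.8) | 60.9 vs 31.1% | 23.0 vs 7.1% | 12.7 vs 3.1% | 76% to 59% |
| (1.2, 0.6) | 62.0 vs 32.1% | 33.5 vs 12.0% | 22.4 vs 6.8% | 86% to 75% |

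The response difference stays at 29.5 to 29.9 points and primary power at about 94%.

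**6. Sensitivity.**
- Truncation: response 63.5–64.1% vs 33.7–34.2%; remission power 64% to 57%, or 86% to 84%.
- Half of patients affected, nearest integer: remission power 52% and 81% at the two ends.
- Count averaging, clean baseline: response 50.8–57.6% vs 23.0–28.1%, power 92–94%.
- Count averaging, baseline affected too: response 58.7–61.8% vs 29.5–31.9%.
- Same-day enema preparation: no effect.

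**The case against.** **The investigator may discount the day.** What is averaged is symptom severity, the diary is for symptoms of colitis, the report at the visit also counts, and an investigator who knows of the preparation can set those stools aside. This stands as a reason why some sites would score sensibly. It does not remove the point, because the text instructs an average over three days and tells nobody to leave one out. Sites would then differ.

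**The size rests on stacked assumptions.** This stands. Preparation the day before, the score given to that day, the rounding rule and the share of patients affected are not in the protocol, and the remission loss moves widely with them.

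**Baseline may be affected too.** This stands. Enrolment lasts only 2 to 7 days and the endoscopy must wait for screening results, which pushes it towards Visit 2. The need for histology pushes the other way. The imbalance is possible, not certain.

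**Stronger readings that the protocol does not support.**
- *The primary test loses power.* A reader could assume an equal relative loss of responders in both arms and find one. The model does not behave that way: at its first setting the loss is (65 − 59.4)/65 = 9% on tralokinumab and (35 − 29.9)/35 = 15% on placebo, so the difference hardly moves.
- *Section 5.6.2 forbids the preparation.* It bans drugs that affect gut function, but section 6.3.2 expressly provides for preparation drugs and their recording, and that specific provision governs.
- *Comparability with other biologics is harmed.* Section 3.2.4 says: "The primary endpoint will be assessed at 8 weeks to provide efficacy results comparable to other biologic drugs". The protocol does not show how those trials treated preparation days, so this cannot be judged.

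**Conclusion.** The point holds as a flaw in a stated scoring rule. With day-before oral preparation, section 6.3.1 as written counts a preparation day in the week-8 stool sub-score and can raise it in improved patients. Both arms are affected and neither is favoured.

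For the primary endpoint, response rates fall somewhat and power is almost unchanged. For remission the loss ranges from small to substantial: 64% to 39–57% at one end of the model and 86% to 75–84% at the other, with all patients affected and daily scores averaged. Among post-baseline visits, partial Mayo is affected at week 8 only.

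Confidence is good on the reading of the text and the direction of the error, and limited on its size. The change is worth making because it removes avoidable misclassification at very little cost, not because the primary conclusion is in danger.

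**What to change.** In section 6.3.1, for both Visit 2 and Visit 6, state that:
- stool frequency and rectal bleeding are averaged over the 3 most recent diary days within the 7 days before the visit, not counting any day on which bowel preparation was taken or endoscopy was performed;
- if fewer than 3 such days exist, the available days are averaged;
- if none exists, the patient's report at the visit of symptoms on the days before preparation is used;
- a fractional average is turned into a whole score by a named rounding rule.

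The fallback is needed because the diary starts at Visit 1, which may be only 2 days before Visit 2. A missing sub-score makes the Mayo score missing (11.1.1), and inclusion criterion 4 then could not be assessed.

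The cost is a few lines in 6.3.1 and one in the diary instructions. Symptoms are already recorded daily and preparation drugs already entered, so there are no added visits, procedures or patients. The small downside is that some scores rest on fewer or slightly older diary days. The endpoint definitions in 11.1.3 to 11.1.5 and section 5.6.2 need no change.
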